13.2.2 Consent through a Legally Authorized Representative (LAR)/surrogate

Some patients who are eligible for this study are likely to not possess decision making capacity. In these cases, consent for study participation may be obtained through a legally authorized representative (LAR) or other surrogate decision maker.

When a patient is identified as eligible for study enrollment, the study team will assess the patient's capacity to make decisions about participation in research. This assessment is completed by a study team member trained in good clinical practice for the conduct of clinical research who is in direct contact with the patient. If the patient cannot meaningfully engage with the study team member (such as, a state of intubation, chemical sedation, and/or not responsive to verbal stimuli), the study team member may consider the patient to lack decision making capacity for consent. If the patient can meaningfully engage

with the study team member, the study team member will explain the APS study to the patient and review the informed consent document with the patient. After this explanation, if the patient cannot describe the basic elements of the study, including risks and benefits of study participation, the study team member may consider the patient as not possessing decision making capacity for consent. The study team member will document the process and outcome of capacity assessment in the APS Study Electronic Data Capture instrument.

If an eligible patient lacks decision making capacity to consent for study participation, the study team may obtain consent for study participation through an alternative decision maker. In this study, we use the term “LAR/surrogate” to indicate the alternative decision maker who is making decisions for the patient while the patient lacks capacity. The US Code of Federal Regulations (CRF) section 46.102(i) defines a legally authorized representative (LAR) as: “an individual or judicial or other body authorized under applicable law to consent on behalf of a prospective subject to the subject's participation in the procedure(s) involved in the research. If there is no applicable law addressing this issue, *legally authorized representative* means an individual recognized by institutional policy as acceptable for providing consent in the nonresearch context on behalf of the prospective subject to the subject's participation in the procedure(s) involved in the research.” The term “LAR/surrogate” is applied to the person making medical decisions for the patient, either as an explicit legally authorized representative or through local policy and custom. The study team should follow local laws and policies when identifying an alternative decision maker for consent for study participation.

If consent for study participation is obtained via an LAR/surrogate, the study team will iteratively assess the patient to evaluate whether the patient has gained decision making capacity. These assessments will be made through hospital discharge or Study Day 14 (whichever occurs first). If the patient is identified as regaining capacity, the study team will obtain consent for study participation from the patient at that time by having the patient sign the consent form that has already been signed by an LAR/surrogate. At that time, the patient may decline to continue participation in future study procedures or withdraw informed consent; details of procedures for withdrawal of informed consent are outlined below.

13.2.3 Rationale for two study protocols with different approaches to informed consent

A key objective of this study is to rigorously phenotype ARDS, pneumonia, and sepsis, among severely and critically ill patients throughout their entire course of illness, beginning immediately when a patient meets eligibility criteria through 12 months later. To achieve this objective, patients must be enrolled as early as possible in their course of illness. Early biospecimens are crucial for the objectives of the APS Consortium. Up to 75% of patients in the ICU experience delirium or altered mental status prohibiting their ability to provide informed consent.²⁶ Frequently, LARs for critically ill adults are not available to provide written informed consent for research participation in a timely fashion. For example, prior work has shown that at a publicly-funded hospital, 18% of eligible patients for ARDS clinical trials are not enrolled due to the patient not having capacity for consent and no LAR/surrogate being available.²⁷

An accompanying protocol (APS Study Protocol B – alteration protocol) will be used when consent for study participation cannot be obtained before study entry. These protocols are linked. Protocol B

describes minimal risk study procedures that may be completed with alteration of informed consent and no written informed consent for study participation. The minimal risk study procedures in Protocol B are identical to study procedures in Protocol A. Protocol B contains a subset of study procedures from Protocol A that are minimal risk.

An approach of using two protocols to enroll participants – one that governs consented patients (Protocol A) and one that governs patients participating under alteration of informed consent (Protocol B) – is being utilized to minimize selection bias that would occur if only patients who were able to immediately provide written informed consent were enrolled. Outlining minimal risk procedures from the APS Study schedule of events in a separate protocol (Protocol B) enables participants without consent to begin minimal risk study procedures using an alteration of informed consent process. Meanwhile, participants with consent completed may engage in all study procedures, including both minimal risk procedures and greater than minimal risk procedures.

Goals of the study team include:

- Early enrollment of a population that represents the patient population of those suffering from ARDS, pneumonia, and sepsis, including those who are critically ill and often unable to rapidly consent for research.
- Obtain informed consent for study participation prior to initiation of study procedures for as many participants as possible.
- For participants who enter the study with alteration of informed consent, obtain written informed consent as soon as possible.

13.2.4 Description of consent procedures for Protocol A and Protocol B

Protocol A (full protocol): This document contained herein is Protocol A. It describes all study procedures that a participant may complete during the course of the APS study and governs study procedures for participants who have completed informed consent for research participation (either directly or through an LAR/surrogate). Protocol A has two accompanying informed consent documents (ICDs):

- ICD #1 (primary study): Informed consent document for the primary APS study, including in-hospital study procedures and long-term outcome surveys. ICD #1 contains two part--part 1, which includes information shared across all sites participating in the study and part 2, which contains local context information for a particular site and signature lines. Participants who entered the study with alteration of informed consent may consent for the full primary study at any time through the 3-month follow-up time point. While the participant is in the hospital, consent will be obtained via ICD #1. If a participant enters the study via alteration of informed consent (Protocol B) and is discharged from the hospital without informed consent being obtained, the study team will attempt to contact the participant at the 3-month study time point to obtain consent. If this contact at the 3-month time point is made via telephone, consent may be obtained with waiver of documentation of signature. Similarly, if a participant had previously been participating in the study via surrogate consent, the patient will be given the opportunity to consent for themselves at the 3-month phone call (“reconsent”) with waiver of documentation of signature. Waiver of documentation of signature will use the following procedures:

- i. study team member explains the study to the participant;
- ii. study team member reviews ICD #1 with the participant;
- iii. study team member provides opportunity for participant to ask questions and answers those questions;
- iv. participant provides verbal confirmation of wanting to participate in the study;
- v. study team member documents this consent process in the Study Electronic Data Capture instrument.

If a participant attends a long-term outcome in-person visit without having previously provided informed consent for study participation, informed consent for study participation will be obtained at that time using ICD#1.

- ICD #2 (LTO in-person visits): Informed consent document for long-term outcome in-person visits. ICD #2 contains two part--part 1, which includes information shared across all sites participating in the study and part 2, which contains local context information for a particular site and signature lines. Participants who attend in-person long-term follow-up visits will complete informed consent for the in-person long-term outcome study procedures prior to initiation of those procedures. This informed consent document for in-person long-term outcome visits (ICD #2) is separate from the informed consent document for the primary study (ICD #1).

Protocol B (alteration protocol): Protocol B is described separately in a dedicated protocol outside this document. It describes a procedure for participation in the APS Consortium study with alteration of informed consent. Protocol B will be used for participants for whom informed consent for the study participation cannot be obtain via the patient or LAR/surrogate prior to initiation of study procedures. Minimal risk procedures within the APS study may be completed using alteration of informed consent. Protocol B outlines the minimal risk procedures that may be completed without informed consent for research. Protocol B has no informed consent document but includes a patient information sheet to help notify patients and others about enrollment in the study.

Participants with informed consent will complete study procedures described in Protocol A (this document), and participants who have not provided informed consent will complete study procedures described in Protocol B (a separate document). Participants without informed consent for study participation will complete a subset of study procedures (described in Protocol B) completed by participants with informed consent for research (described in Protocol A). Participants who enter the study on the alteration of informed consent protocol (Protocol B) will be iteratively approached for consent; if and when informed consent for participation in the APS Study is obtained, the participant will be moved from Protocol B to Protocol A (Figure 2).

Greater than minimal risk procedures may be completed after informed consent is obtained among participants who started study participation under alteration of informed consent procedures. Patients who move from Protocol B to Protocol A will seamlessly continue on the APS Study schedule of events and maintain the same Study Day structure initiated at study entry. Study days continue through the transition from Protocol B to Protocol A; that is, if a patient provides informed consent on Day 4, study procedures

completed on Protocol B for Day 0 through Day 3 will remain unchanged and Study Day 4 procedures will pick up on Protocol A.

For participants who enter the study with alteration of informed consent, study team members will attempt to obtain informed consent while the patient is in the hospital through Study Day 14 and at the 3-month time point.

Data and biospecimens collected under Protocol A and Protocol B will be pooled for storage and analysis.

13.2.5 Withdrawal of informed consent

If a participant or LAR/surrogate indicates an intention to withdraw informed consent for study participation or forego future study procedures, the study team will clarify the wishes of the participant/LAR/surrogate and categorize the request into one of the following categories. Steps to honor wishes of the participant/LAR/surrogate are outlined for each category.

- (i) Category 1 Request: Complete withdrawal of consent, including destruction of identifiable data and biospecimens and no participation in any future study procedures.

Action: The study team will note in the study data capture instrument that the participant or LAR/surrogate withdrew consent. An attempt will be made to understand and document why the participant withdrew consent. No additional study procedures will be performed. Identifiable participant data will be removed from the data capture instrument. Biospecimens that are stored at the enrolling site and APS Coordinating Center will be destroyed. Deidentified data and biospecimens that have been transferred to NIH repositories or to laboratories for analysis may not be able to be destroyed. Completed works, such as manuscripts, that used the participant's data and/or biospecimens will not be revised or retracted and data to support those works will be retained.

- (ii) Category 2 Request: Previously collected data and biospecimens may be retained but desire expressed to not participate in future direct-contact study procedures.

[figure not shown]
Action: The study team will note in the study data capture instrument that the participant or LAR/surrogate maintains consent for the study but requested no additional direct contact study procedures. The study team will attempt to understand and document why the participant requested to stop additional direct-contact study procedures. The study team will not perform any additional procedures that involve direct contact between study personnel and the participant, including interviews, biospecimen collection, long-term outcome surveys, and in-person long-term outcome visits. Medical record data capture will continue. All collected data and biospecimens will be used.

- (iii) Category 3 Request: No participation in some specific study procedures but willingness to participate in other study procedures.

Action: The study team will work with the participant/LAR/surrogate to understand what specific procedures the participant/LAR/surrogate wants to avoid in the future. The study team will note in the data capture instrument which study procedures will not be completed and why the participant/LAR/surrogate requested to opt out of those procedures. The study team will avoid the specific study procedures as requested, such as future blood draws, future swabs, future interviews/surveys, or future in-person visits. All collected data and biospecimens will be used.

Figure 2. Flow diagram of informed consent procedures.

13.3 Human subjects considerations for data and biospecimen banking and sharing

13.3.1 Disclosure of research results to participants

Results for CT scans completed at the 12-month visit for research purposes will be disclosed to participants via site investigators. The investigators do not intend to disclose the results of other research testing to participants.

13.3.2 Storage of data and biospecimens

Data collected as part of the Consortium-wide study, including those captured from the EHR and other hospital databases, will be transferred into the study database via standardized electronic case report forms (eCRFs), which will reside in a centralized database located on secure servers. Study data will be entered and accessed via a secure, password-protected REDCap database website wherein all web-based information is encrypted. REDCap was developed specifically around HIPAA Security guidelines and is recommended by both the Vanderbilt University Privacy Office and Institutional Review Board. REDCap is available to all sites participating in the APS Consortium.

Data transferred to the APS Coordinating Center will include dates (for example, hospital admission date, and date of birth) and contact information to facilitate post-hospital follow-up visits. Biospecimens will be labeled with a study identification number without patient name, medical record number, or date of birth. Access to personal health information in study databases will be limited to only those individuals requiring that level of access.

Study data and biospecimens will be stored for an indefinite period of time for future use. Deidentified data and biospecimens will be shared with researchers outside the APS Consortium. For long-term storage of data, personal identifiers will be removed once quality assurance has been confirmed and prior to data lock. All research records will be accessible for inspection by authorized representatives of the IRB, federal regulatory agency representatives, and NIH representatives.

13.3.3 Sharing data and biospecimens

The APS Consortium will develop data management and sharing plans consistent with NIH policies (<https://sharing.nih.gov/>).

APS Consortium investigators will be permitted to access and use data and biospecimens for the purpose of achieving the Consortium-wide and center-specific project aims directly from the Consortium Coordinating Center. Consortium-wide biospecimens and data will be sent to the central biorepository and study database housed at the Consortium Coordinating Center. Investigators seeking to perform approved ancillary studies with data and/or biospecimens collected by the APS Consortium may request data and biospecimens from the Consortium Coordinating Center before data and biospecimens are deposited in BioData Catalyst and BioLINCC.

Ultimately, the Consortium Coordinating Center will deposit de-identified data and biospecimens in BioData Catalyst and BioLINCC. Once data and biospecimens reach BioData Catalyst and BioLINCC, they will be available to investigators through the governance of BioData Catalyst and BioLINCC without involvement of the Consortium Coordinating Center.

13.3.4 Co-enrollment with other studies

The APS Consortium steering committee, OSMB, and NHLBI will agree on co-enrollment procedures before participants in the APS study are co-enrolled with other studies. Principles for co-enrollment will include the following:

- Co-enrollment should not affect the scientific goals of the APS Consortium. Co-enrollment will not be permitted if it compromises the scientific integrity and/or statistical power of APS Consortium studies.
- Co-enrollment will be compliant with NIH and NHLBI guidelines and policies.
- Co-enrollment will only be allowed when study procedures for the APS Consortium studies can be achieved. Co-enrollment in the APS Consortium will not be permitted when study procedures in a co-enrolled study would prevent completion of data or biospecimen collection for the APS Consortium study.
- Safe blood collection procedures for critically ill patients will be followed as detailed by the PETAL Network Investigators.²⁸

14. Adverse Events and Safety Monitoring

14.1 Overview of Safety Monitoring

In this observational study that uses routine techniques for data and biospecimen collection, substantial numbers of serious, study-related adverse events are not anticipated. The study will not be overseen by the US Food and Drug Administration (FDA). Safety monitoring will be performed by the investigators, the study's single IRB at Vanderbilt University Medical Center, and an NHLBI-appointed Observational Safety Monitoring Board (OSMB).

14.2 Adverse Events

14.2.1 Paradigm for collecting Adverse Events

In this study, investigators will collect and report adverse events (AEs) that are classified as serious and related to study procedures, those prespecified as adverse events of special interest (AESIs), and those that potentially change the risk: benefit balance for patient participation (Unanticipated Problem (UP)). AEs that meet at least one of the following three criteria will be collected in this study:

- 1) both serious and study related;
- 2) AESI;
- 3) UP.

AEs that do not meet any of these criteria will not be collected.

Events that meet criteria for an AE in the population enrolled in this study will be numerous due to the severe medical conditions these patients have. The proportion of AEs experienced by the study population that are related to study procedures is anticipated to be extremely small. Thus, the paradigm of AE collection and reporting in this study was designed to capture all the events that could potentially represent a safety concern for the study while avoiding overly burdensome AE monitoring for participants, study teams, the IRB, and OSMB.

14.2.2 Definitions for Adverse Events

(i) Adverse Event

An AE is defined as any untoward medical occurrence.

(ii) Serious Adverse Event (SAE)

A serious AE (SAE) is an untoward medical occurrence that directly causes at least one of the following in the judgement of the study team:

- Death
- Life-threatening condition that places the participant at immediate risk of death
- Inpatient hospitalization or prolongation of existing hospitalization
- A persistent or significant incapacity or substantial disruption of the ability to conduct normal life functions or a congenital anomaly/birth defect.
- An important medical event not meeting the criteria for one of the outcomes above but, based on medical judgment, jeopardized participant safety or required medical or surgical intervention to prevent one of the outcomes listed in this definition.

(iii) Relatedness of SAEs

SAEs will be evaluated for relatedness to study procedures using the definitions below:

- **Definitely Related:** The adverse event meets all three of the following criteria: (a) a temporal sequence from study procedure to the adverse event suggests relatedness, (b) the event cannot be explained by the known characteristics of the participant's clinical state or therapies, and (c) evaluation of the participant's clinical state indicates to the study team the experience is definitely related to study procedures.
- **Possibly Related:** In the study team's opinion, the adverse event has a reasonable possibility of being related to study procedures but one or more of the above criteria for "Definitely Related" are not met.

- Probably Not Related: The adverse event occurred at a time when it could have been caused by study procedures but, in the opinion of the study team, can reasonably be explained by the known characteristics of the participant's clinical state or therapies.
- Definitely Not Related: The adverse event was definitely produced by the participant's clinical state or therapies and not by the study procedures.
- Uncertain Relationship: The adverse event does not meet any of the criteria outlined above and the study team cannot ascertain enough information to classify relatedness of the event.

For the purposes of this study, an adverse event is considered related to study procedures if there is a "reasonable possibility" of a causal relationship between a study procedure and the adverse event or the relationship cannot be determined; this includes events that are classified as definitely related, possibly related, or of uncertain relationship.

(iv) Adverse events of special interest (AESIs)

An adverse event of special interest (AESI) is defined as a pre-specified event of scientific or medical concern that has the potential of being related to study procedures and is important to understand regardless of investigator classifications. In this trial, AESIs listed below will be recorded as an AE and will require a written narrative regardless of a site's study team classification of seriousness and relatedness. For this study, the following events are AESIs:

- **AESI #1**: New or worsening hypoxemia within 30 minutes of a study-specified NBBAL. For AESI consideration, new or worsening hypoxemia is defined by the event meeting both of the following criteria: (i) a decrease in SpO₂ by at least 10 percentage points in the time window between the beginning of the procedure and 30 minutes after the procedure is completed; and (ii) a persistent absolute increase in FiO₂ by at least 10% for at least 6 hours after the procedure compared to before the procedure.

(v) Unanticipated Problem (UP)

[figure not shown]
An unanticipated problem is a finding discovered during the conduct of the study that suggests participation in the study may have more risk than was anticipated at the time of study initiation. UPs have the potential to change the risk: benefit balance of the study compared to what was known at the time of study launch.

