Tracheal aspirate fluid collection	Bleeding, localized pain, drop in oxygen levels (hypoxemia), and dislodgement of the tracheal tube. A drop in oxygen levels from tracheal aspirate collection is very unlikely to cause patient harm.	Only study or clinical personnel trained in the collection of tracheal aspirate fluid will collect this specimen. Tracheal suctioning is a routine clinical procedure and tracheal aspirates for this protocol will be done at times that tracheal aspirates are being collected as part of clinical care, whenever possible.
NBBAL procedure	Bleeding, localized pain, dislodgement of the tracheal	Only study or clinical personnel trained in the NBBAL procedure will complete this procedure for the study. NBBAL

Study procedure	Potential risks	Study methods to minimize risks
	tube, and drop in oxygen levels (hypoxemia), which if severe and uncorrected, can lead to organ injury and death. Serious injury from a NBBAL is rare (<1%). ²³	is a common clinical procedure in some hospitals. Only patients who are intubated will undergo the NBBAL procedure. Only patients who pass a pre-procedural safety screen under the supervision of the site investigator will undergo a NBBAL. Hypoxemia temporally related to a study NBBAL procedure will be collected as an AESI and reported to the sIRB and OSMB.
Long-term outcome surveys (via phone, SMS, or email)	No plausible physical risks. Participants might experience embarrassment or emotional discomfort.	Participants do not have to answer any questions that make them feel too uncomfortable. An on-call mental health specialist will be available to talk with patients that have severe emotional stress or suicidal thoughts.
Short physical performance battery (SPPB) [at in-person LTO visits]	SPPB assesses lower extremity functioning. It includes a balance test, a timed 4-meter walk test, and chair stand test. There is a small risk of falling. Activities may increase heart rate.	The testing will be performed by trained study staff. Movements are completed in a standard order, starting with easier movements. Participants will be able to skip any movement that they cannot do or feel would be unsafe to try.
CNS-Vital Signs [at in-person visits]	CNS vital signs is a computer based cognitive assessment. Participants might experience embarrassment or emotional discomfort from not being able to answer some questions.	Participants do not have to answer any questions that make them feel too uncomfortable.

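### 'Possibly Related' and 'Probably Not Related' overlap in 14.2.2(iii), and of the serious NBBAL risks in Table 13 only hypoxemia is recorded whatever label the site gives

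*Protocol*

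**What the plan says.** Section 14.2.1 limits collection to events that are both serious and study-related, AESIs, and unanticipated problems. Of everything else it says "AEs that do not meet any of these criteria will not be collected". It describes the scheme as "designed to capture all the events that could potentially represent a safety concern" while sparing participants, sites and oversight bodies an excessive monitoring load.

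Section 14.2.2(iii) gives five relatedness classes. Three matter here:

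- **Definitely Related** has three criteria, one of which is "b) the event cannot be explained by the known characteristics of the participant's clinical state or therapies".
- **Possibly Related** is again a judgement by the site. Its wording is "the adverse event has a reasonable possibility of being related to study procedures but one or more of the above criteria", where the criteria meant are those of the definite class, at least one of which has failed.
- **Probably Not Related** means "The adverse event occurred at a time when it could have been caused by study procedures" but, in the team's opinion, it "can reasonably be explained by the known characteristics of the participant's clinical state or therapies".

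The paragraph after the classes treats an event as related when a causal link is reasonably possible or cannot be determined. It names the definite, possible and uncertain classes as falling within this. 'Probably Not Related' is not named.

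Section 14.2.2(iv) lists one AESI, hypoxemia after a study NBBAL. In section 13.1, the NBBAL row of Table 13 lists "Bleeding, localized pain, dislodgement of the tracheal" tube, and hypoxemia. Its mitigation column promises AESI collection for hypoxemia only.

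**The concern.** The fact that moves an event from 'Definitely' down to 'Possibly' (illness could explain it) is also the main ingredient of 'Probably Not'. In ventilated patients with sepsis, pneumonia or ARDS, an illness explanation is often available. Section 14.2.1 itself expects adverse events to be numerous because of the underlying disease. Two sites could therefore give different labels to the same serious event, each in line with the text. One event would be narrated and sent to the single IRB and NHLBI, and from there to the monitoring board. The other would have no adverse event form.

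The AESI mechanism exists to remove this dependence on site judgement, but it covers only one of the serious physical risks that Table 13 names for NBBAL. At stake is how consistently airway bleeding and tube dislodgement after a research-only invasive procedure are counted across sites.

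**Working it through.** The plan gives no figure to reproduce on this point. The check is a logical one on the definitions, followed by a simple statement of scale.

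**1. Do the definitions overlap?** Code four yes/no judgements from 14.2.2(iii): T, timing compatible with the procedure; E, reasonably explained by illness or therapy; R, reasonable possibility of relatedness; D, team judges it definitely related. Then:

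- Definitely = T and not E and D
- Possibly = R and not Definitely
- Probably Not = T and E

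If T = 1 and E = 1, Definitely is false whatever D is, so Possibly reduces to R. Every case with T = E = R = 1 meets both Possibly and Probably Not. That is 2 of the 16 combinations (D = 0 and D = 1). The count shows that the overlap exists; it says nothing about how often it would occur.

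**2. Does another class catch these cases?** No. 'Uncertain Relationship' applies only when none of the other definitions is met, and here two are met.

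**3. What follows from each label, for a serious event?**

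| Label | Counted as related (14.2.2) | Collected (14.2.1) |
|---|---|---|
| Possibly Related | Yes | Yes |
| Probably Not Related | Not among the named classes | Only if an AESI or unanticipated problem |

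**4. Do the other two routes cover bleeding and dislodgement?**

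- *AESI #1* needs both an SpO2 fall of at least 10 percentage points by 30 minutes after the procedure and an absolute FiO2 increase of at least 10% lasting at least 6 hours. A bleed or dislodgement that produces this pattern is recorded; one that does not is outside the AESI.
- *Unanticipated problem* means a finding that suggests more risk than was foreseen at study start. Table 13 already lists both harms, so a single case would not clearly qualify.

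**5. Scale.** Table 9 and section 16.3.8 plan about 700 NBBALs. Table 13 puts serious injury below 1%.

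- 0.01 × 700 = 7, so fewer than 7 serious injuries are implied.
- At assumed rates of 0.5% and 0.25%: 0.005 × 700 = 3.5 and 0.0025 × 700 = 1.75.
- One event recorded or not: 1/700 = 0.14 percentage points.

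With counts this small, the label given to one or two events visibly changes the observed rate.

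**The case against.** The strongest reply is that the protocol already supplies the governing rule. The paragraph after the five classes makes any reasonable possibility of a causal link sufficient for relatedness, and the list of classes that follows can be read as illustrating that test. An event that fits both labels would then be related and reported. Further, on an ordered scale a team that chooses 'Probably Not' is saying that it sees no reasonable possibility, and real doubt goes to 'Uncertain', which counts as related. Much of this stands: the general test favours reporting. But the class wording does not carry it, and the text then works from the assigned class without saying which prevails.

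Figure 3, the flow diagram for reporting decisions, is not available in the text reviewed. It may contain an order of precedence, so the absence of one cannot be asserted.

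A reader might infer that such events vanish from the study altogether. The documents do not support that. Table 4 collects vital signs, laboratory values, ventilator data and blood products daily to Day 7, together with organ failures and mortality. What would be missing is the adverse event form, its narrative and the link to the procedure.

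Two further points are fair. The NBBAL safety screen in 8.2.2 excludes frank hemoptysis, therapeutic anticoagulation and low platelets, and a dislodgement during catheter passage is hard to blame on illness; both narrow the room for an illness explanation. And selective collection is deliberate: the sentence in 14.2.1 states an aim balanced against burden and is not a guarantee. Leaving non-serious events uncollected is part of that design and is not at issue.

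**Conclusion.** The point holds in a limited form. The two definitions are not mutually exclusive. A serious event labelled 'Probably Not Related' has no study adverse event record unless it is an AESI or an unanticipated problem. For airway bleeding and tube dislodgement after NBBAL, capture therefore depends on the site's label, whereas hypoxemia meeting the AESI definition is recorded regardless.

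The size is modest: fewer than 7 serious injuries implied among about 700 procedures, each worth about 0.14 percentage points. This rests on the planned 700 and the stated rate below 1%.

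A reader might go on to infer that NBBAL harm will be under-reported by some given fraction, or that the monitoring board cannot judge the procedure's safety. Neither follows. The documents give no mislabelling rate, the general test leans towards reporting, and section 14.3 has the board monitor safety and data completeness. This is a wording gap and a gap in the AESI list that are cheap to close; it is not evidence that harms are being lost.

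**What to change.** 1. In 14.2.2(iii), state that 'Probably Not Related' applies only when no reasonable possibility of relatedness remains, and that 'Possibly Related' prevails when both descriptions fit. This carries the section's own general test into the class definitions. Check that Figure 3 agrees.
2. In 14.2.2(iv), add airway bleeding and tube dislodgement temporally related to a research NBBAL to the AESI list. The investigators should set the severity threshold and time window, which the documents do not supply for these events. Align the mitigation text in Table 13, and report these events against the number of NBBALs performed.

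The cost is protocol and case report form wording, plus a few extra event forms in about 700 participants, some for events that prove unrelated. Selective collection stays as it is for all other procedures.
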